Neurostimulation & Depression Study

Protocol Summary Document for ProofPilot Remote Studies

ProofPilot Study ID:2518

Principal Investigator

[name]

Study Purpose

Examine the safety and effectiveness of the Fisher Wallace Cranial Electrotherapy Stimulator Device on Major Depressive Disorder using two 20-minute per day treatment sessions over eight weeks.

Study Design

This is a fully remote trial where participants engage at home in the study using the ProofPilot study platform. All potential participant enrollment data, including proof of identity via government ID will be reviewed by licensed medical professionals in the participant's state prior to their full enrollment.

Participants will be randomized into an immediate or delayed treatment arm. The immediate treatment arm participants will be shipped an active Fisher Wallace device limited to Level 2 output even if a participant raises the dial beyond that. The participant will remain with the active device for the full 8 weeks.

In the delayed treatment arm, the participants will receive a sham device that looks exactly the same, but only provides treatment for 2 seconds. At week 4, sham arm participants will be unblinded and shipped an active device (limited to Level 2 output even if a participant raises the dial beyond that). The delayed arm participants will continue with active devices for the remaining 4 weeks of the trial.

Physicians, via a telemedicine visit, will diagnose participants, prescribe the device and provide medical oversight. Participants will self-report adherence and any adverse events on a daily basis through diaries. Self-report outcomes will be collected via online assessments at baseline, 2-week point, 4-week point and 8 week points. In addition, physicians will also conduct an assessment at baseline and week 4.

Weeks 1-4 of this protocol are intended to provide sufficient evidence of safety and effectiveness to support the FDA Premarket approval submission for the Fisher Wallace CES device. Data collected in weeks 5-8 of this protocol, relevant to an ongoing evaluation of safety and effectiveness, may be submitted to FDA in the form of an update report, in accordance with 21 CFR § 814.20(b)(13)(e).

Treatment Instructions

After receiving a prescription via remote asynchronous telemedicine, the patient is randomized to either an immediate or delayed treatment arm, and delivery of the Fisher Wallace device will be made by UPS/Fedex/UPS. Upon delivery (as identified by shipment tracking code), individuals will be presented with video how-to instructions, and treatment overviews (along with some device usage troubleshooting facts). The device packaging will also include instructions. A PDF version of the instructions, along with FAQs will be made available via ProofPilot for quick reference.

Participants will be directed to use the device twice per day for 20 minutes, once soon after waking up, and the second time per day 20 minutes prior to attempting sleep.

The study timeline will commence upon completion of the first treatment as identified by the participant in ProofPilot.

Participants who have questions about the device will be referred to ProofPilot customer support. All queries will be logged and reported at the end of the study. ProofPilot will refer those questions that can not be answered with an automated frequently asked questions system to PI [name] and/or the manufacturer (Fisher Wallace) for follow-up.

Primary Outcome Measures:

- Change in Beck Depression Inventory Score in “Treatment week 4” versus Baseline in immediate versus delayed arm.

Secondary Outcome Measures:

- Change in Hamilton Depression Rating Scale from Baseline to “Treatment week 4” in immediate versus delayed arm.
- Change in Beck Depression Inventory Score in “Treatment week 2” versus Baseline in immediate versus delayed arm.
- Change in Patient Health Questionnaire - 8 (PHQ-8) score at “Treatment week 4” versus Baseline in immediate versus delayed treatment arm.
- Change in Patient Health Questionnaire - 8 (PHQ-8) score at “Treatment week 2” versus Baseline in immediate versus delayed treatment arm
- Change in Beck Depression Inventory Score from “Treatment Week 4” to “Treatment week 8” in delayed treatment arm (once they have started use of the actual device).
- Device safety, tolerability and adherence over 8 week period as measured by SAFTEE

Sample Size:

Sample size for the study is based on the primary outcome measure of PHQ-8. The difference between the randomized treatment control subjects for the change in score from “Treatment Week 4” versus baseline will be compared with a two-sample t-test at the one-sided 0.025 alpha level. For a planned sample size of 175 total subjects with 1:1 allocation, the study will provide 80% power for an effect size of 0.426 where effect size is based on the ratio of the difference of means over the standard deviation.

p value: two-sample t-test at the one-sided 0.025 alpha level

Statistical Analyses:

Primary analyses of primary and secondary outcome measures will be based on the comparison of the randomized groups via t-tests for means for the change from baseline. Sensitivity analyses for the assumption of normality and for the impact of missing data will be performed. Subgroups results based on sex and race will be provided.

Inclusion/Exclusion

- Age greater than or equal to 21
- US resident
- Can receive packages to their home via UPS/Fedex/USPS
- Major Depressive Disorder
- PHQ-8 Score greater than 10 (show some signs of mild to moderate depression)
- PHQ-8 Score less than 20 (given remote study serious depressed should be excluded)
- Read/write English
- have not contemplated suicide in the past year
- not been institutionalized for mental health issues.
- not currently experiencing problems with alcohol or drug abuse
- can commit to not drinking alcohol 4 hours before bedtime for the duration of the study
- can commit to two (2) 20 minute sessions per day for 8 weeks
- has not used a brain stimulation treatment in one year
- no suspected or known history of heart disease
- no pacemaker
- not under medical supervision for other serious medical condition
- not taking opioids
- are a resident of states in which we have licensed medical professionals
- Any co occurring significant psychiatric disorder that would impair participant's participation
- any use of illicit drugs

Those with a PHQ-8 score greater than 20 will be directed to contact local mental health assistance and will be provided with the National Suicide Prevention Hotline number for immediate assistance.

Recruitment

Individuals in the study will be recruited in two forms targeted to the states in which we have contracted with licensed medical professionals.

- Fisher Wallace email marketing to patients who have not purchased a Fisher Wallace device and to providers who may refer patients to the study
- Digital advertising on GoodRx, Facebook, Instagram, Google and other common advertising platforms
- Physician referrals.

All potentially interested participants will be directed to the ProofPilot study recruitment page for registration and screening to begin the study.

Study Design/Methods

All participants upon expressing interest, will be asked to create an account on ProofPilot, and answer some basic demographic questions. (Birthdate, location, sex, timezone, preferred language).

All study activities, except those with the Fisher Wallace device itself, will be completed on ProofPilot. ProofPilot is available across any internet connected device with a reasonable screen size. No download is required.

At enrollment, the participant will be asked a series of screening questions, will complete the PHQ-8, the Beck Depression Inventory and a self administered version of the MINI.

Eligible individuals who will be self consented online, will then be asked to take a photograph with their mobile device of a government issued ID for identification. Participants will set an appointment on ProofPilot with a licensed telemedicine psychiatrist in their state within the next several days.

At that virtual visit, the physician will review the participant's responses to the MINI, and add several additional elements that require a physician assessment. Then the physician will administer the HAM-D - and make a final determination if the participant is a good for the study and authorize a prescription for the device.

Participants will then complete additional baseline measures including the QIDS-SR, PROMIS Sleep Disturbance, and Jenkins Sleep Scale. They will then enter in shipping information to place an order for the Fisher Wallace Device.

All participants will be randomized, with a 50/50 chance, into a control arm or active treatment arm. Control arm participants will receive an active treatment device at the end of week 4. This is a double blind design, the participants, nor any study staff, except those conducting fulfillment are aware of which arm the participant is in until unblinding at the end of the study.

Eligible individuals will then be asked to take a photograph with their mobile device of a government issued ID for identification. They will then enter in shipping information to place an order for the Fisher Wallace Device.

Participants will then complete additional baseline measures including the QIDS-SR, PROMIS Sleep Disturbance, and Jenkins Sleep Scale.

Meanwhile, collected data from PHQ-8, and the Beck Depression Inventory along with proof of identification will be reviewed by medical oversight licensed in the state in which the participant resides and the order released with a prescription for the device. An appointment will be made for the physician to meet with the patient over video telemedicine. During this visit, the physician will evaluate the patient using previously collected baseline data, and their own assessments (MINI, HAM-D) to ensure proper diagnosis and set a professional assessment baseline.

Should the physician feel the participant is a good match, they will issue the prescription for the Fisher Wallace device.

Shipments will be fulfilled by the sponsor's fulfillment capacity by individuals who are not affiliated with the study. All study staff, including remote physicians, will be blinded to who receives the sham and who receives the active device. Tracking information from UPS/Fedex/USPS will trigger tasks based on where the shipment is in the fulfillment process, including at delivery.

At delivery, ProofPilot will automatically trigger instruction tasks, a treatment expectancy survey, and a notification to "Start the trial." The "Start the trial" task will trigger the 2 week, 4 week and 8 week follow up points key to the outcome measures. It will also trigger the window period for the final (week 4) participant/physician video teleconference assessment.

Participants will receive a daily treatment diary at 6:45AM (though they may complete it anytime within an 18 hour period). The daily treatment diary will ask about treatment adherence and any adverse events from the prior day and provide a morning treatment reminder. Participants will also receive an evening

treatment reminder at 7:15PM. Reminders will be presented from ProofPilot in the morning and in the evening adjusted for the participant timezone.

At the end of the study, participants will need to return both the active and sham devices to qualify for compensation.

At the 2 week, 4 week and 8 week (unless otherwise noted) time point from “Start of Trial” participants will repeat baseline measures:

- **PHQ-8:** Covers the DSM-IV criteria for major depressive disorder with a discriminant validity of .89 to .92^{1,2}
- **Beck Depression Inventory:** 21-question multiple-choice self-report inventory, one of the most widely used psychometric tests for measuring the severity of depression.
- **MINI:** The M.I.N.I. was designed as a brief structured interview for the major Axis I psychiatric disorders in DSM-IV and ICD-10. Validation and reliability studies have been done comparing the M.I.N.I. to the SCID-P for DSM-III-R and the CIDI (a structured interview developed by the World Health Organization for lay interviewers for ICD-10). The results of these studies show that the M.I.N.I. has acceptably high validation and reliability scores, but can be administered in a much shorter period of time (mean 18.7 ± 11.6 minutes, median 15 minutes) than the above referenced instruments. It can be used by clinicians, after a brief training session. Lay interviewers require more extensive training. The MINI is used in a participant self-administered format, and will be reviewed during a telemedicine visit with a licensed physician to help diagnose major depressive disorder and rule out other mental health disorders.
- **Hamilton Rating Scale for Depression (HAM-D)** (at baseline and 4 week point only): Used by physicians to rate the severity of participant's depression symptoms.
- **QIDS-SR (Quick Inventory of Depression Symptoms):** Nine DSM-IV-TR criterion symptom domains are evaluated to diagnose major depressive disorder (MDD). The Quick Inventory of Depressive Symptomatology (QIDS) provides an efficient assessment of these domains. We are using the Self Report version.
- **Jenkins Sleep Scale** (30 day measure so will skip week 2). Designed as an efficient and brief instrument for use in research, the four-item question evaluates the frequency and intensity of certain sleep difficulties in respondents. With only four items, it cannot begin to address the entire spectrum of sleep disorders and should only be considered for use as a preliminary screening device, and is therefore used in conjunction with PROMIS Sleep Disturbance.
- **Promis Sleep Disturbance:** The PROMIS-SD had greater measurement precision than the Pittsburgh Sleep Quality Index (PSQI) and the Epworth Sleepiness Scale (ESS) as indicated by larger test information values across the continuum of severity, despite having fewer total items, a major advantage for both research and clinical settings.³
- **COMBINE SAFTEE** (systematic assessment for treatment of emergent events modified for mental health and substance abuse)

The blue bar indicates shipment/delivery of the active or sham device.

¹ Kroenke, Kurt; Spitzer, Robert L; Williams, Janet B W (2017-05-31). "The PHQ-9". Journal of General Internal Medicine. 16 (9): 606–613. doi:10.1046/j.1525-1497.2001.016009606.x. ISSN 0884-8734. PMC 1495268. PMID 11556941

² Löwe, Burnd; Spitzer; Gräfe; Kroenke; Quenter; Zipfel; Buchholz; Witte; Herzog (February 2004). "Comparative validity of three screening questionnaires for DSM-IV depressive disorders and physicians' diagnoses". Journal of Affective Disorders. 78 (2): 131–140. doi:10.1016/s0165-0327(02)00237-9. PMID 14706723.

³ A. John Rush, Ira H. Bernstein Development of short forms from the PROMISTM sleep disturbance and Sleep-Related Impairment item banks, Behav Sleep Med. 2011 Dec 28; 10(1): 6–24. doi: 10.1080/15402002.2012.636266 PMCID: PMC3261577 NIHMSID: NIHMS335121 PMID: 22250775

	Enroll	Baseline		2-Week	4-Week	8 Week
Inclusion/Exclusion	X					
Consent						
PHQ-8	X			X	X	X
Beck Depression Inventory	X			X	X	X
M.I.N.I Screen	X					
HAM-D	X				X	
Physician Telemedicine Visit	X				X	
Randomization	X					
Treatment Expectancy			X			
Instructions			X			
Quick Inventory of Depressive Symptomatology (QIDS-SR)		X		X	X	X
Jenkins Sleep Scale		X			X	X
Promis Sleep Disturbance		X		X	X	X
COMBINE SAFTEE				X	X	X
Final Feedback & Tolerability						X
Daily treatment adherence and adverse events						

Adverse Event Reporting & Medical Oversight

Licensed medical providers in the state in which the participant lives will provide medical oversight for this effort.

Adverse events will be collected qualitatively via customer support in the ProofPilot platform. In addition, medical oversight staff will automatically receive alerts if participants have a PHQ-8 score over 20 at the 2 week, 4 week or 8 week point. Those participants will also receive notifications to contact local medical support.

Participants will complete the COMBINE SAFTEE at the 2 week, 4 week and 8 week mark to provide additional data for safety and tolerability not otherwise collected.

All adverse events will be followed up upon and tracked in ProofPilot.

Participant Compensation

Participants may earn up to \$100 for participation in the study.

- \$10 Visa Gift Card for Baseline through completing first Fisher Wallace Treatment (aka 'Start Task') as identified above..
- \$90 presented within 2 weeks of study completion (as defined by return of both the active and shame devices) based on the following:
 - \$20 for each 2 week check in (up to \$60)
 - Up to \$30 as calculated by percentage of daily diaries completed over the 8 weeks

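### Nothing in the protocol shields the physician rating the week-4 HAM-D from arm-suggestive remarks at the visit, or places that rating before the sham arm is unblinded

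*Protocol*

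**What the plan says.** **Roles.** Study Design assigns physicians several tasks: "Physicians, via a telemedicine visit, will diagnose participants, prescribe the device and provide medical oversight". It continues: "In addition, physicians will also conduct an assessment at baseline and week 4". In the list of measures under Study Design/Methods, the HAM-D is described as "Used by physicians to rate the severity of participant's depression symptoms", at baseline and week 4 only.

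**Outcome.** The first secondary outcome is "Change in Hamilton Depression Rating Scale from Baseline to “Treatment week 4” in immediate versus delayed arm". The primary outcome (BDI) and the other listed efficacy outcomes (BDI and PHQ-8 at various times) are self-reported.

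**Blinding.** Study Design/Methods states: "All study staff, including remote physicians, will be blinded to who receives the sham and who receives the active device". An earlier paragraph of that section says that only those handling fulfillment know the arm until unblinding at the end of the study. Study Design, by contrast, unblinds sham participants at week 4, when an active device is shipped to them. The week-4 physician visit is given a window, with no stated order relative to that unblinding.

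**Oversight and alerts.** Under Adverse Event Reporting & Medical Oversight: "Licensed medical providers in the state in which the participant lives will provide medical oversight for this effort", and "medical oversight staff will automatically receive alerts if participants have a PHQ-8 score over 20 at the 2 week, 4 week or 8 week point".

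**The concern.** The primary endpoint is self-rated, and the sham delivers output for only 2 seconds, so participants may be able to guess their arm. The HAM-D is then the trial's main check that a self-reported benefit is more than expectation. That check is only as good as the rater's independence from the participant's impressions of the device.

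The physician role combines clinical care with outcome rating, and the rating is made at a video visit where device experience and side effects are natural topics. If the rater hears that the device seems to do nothing, or that it causes sensations, before scoring, the score can absorb the same expectation as the self-report. Agreement between BDI and HAM-D would then look like corroboration without being independent. The risk is greater if the participant has already been told the arm when the visit takes place. Study Design says weeks 1-4 are meant to support a premarket approval submission, so the week-4 HAM-D is likely to be read as supporting evidence.

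**Working it through.** **1. Passages side by side**

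| Question | What the protocol gives |
|---|---|
| Who rates the week-4 HAM-D? | Physicians, who also diagnose, prescribe and provide oversight (Study Design; list of measures) |
| Is a separate rater named? | No |
| Are physicians blinded? | Yes, stated generally; the mechanism given is shipment by people not affiliated with the study (Study Design/Methods) |
| Is the order of the week-4 visit fixed, or the rater's view of follow-up data limited? | Neither is stated |
| When is the sham arm unblinded? | Week 4 (Study Design) or end of study (Study Design/Methods) |
| When is the week-4 visit? | In a window triggered by the start-of-trial task |
| Who gets PHQ-8 alerts? | Medical oversight staff, for scores over 20 |

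Separate fulfillment conceals allocation from staff. It does not govern what a participant says on video. If the 2 seconds apply to each session, the sham runs for 2 / (20 × 60) = 0.17% of a 20-minute session, so remarks about the device could suggest the arm.

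**2. How far the alerts reach**

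Entry requires "PHQ-8 Score less than 20 (given remote study serious depressed should be excluded", so on whole-number scores the highest entry score is 19 and the lowest alerting score is 21. An alert therefore requires a rise of at least 21 − 19 = 2 points past the entry ceiling. Alerts should concern a minority, and an alert does not state the arm.

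**3. The plan's own power figure**

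Inputs from Sample Size: 175 subjects, 1:1, one-sided alpha 0.025, effect size 0.426. With 87 and 88 per arm:

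- SE of the arm difference = √(1/87 + 1/88) = 0.1512 SD
- Degrees of freedom = 87 + 88 − 2 = 173
- Noncentrality = 0.426 / 0.1512 = 2.82
- Power (noncentral t) = 0.800, matching the stated 80%

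**4. Illustration of what a rating bias would do**

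The protocol gives no figure for rating bias, so the values of b below are assumptions. Here b is the average difference between arms, in SD units, that arises from the rating process alone. It assumes no true effect and all 175 participants rated. The rejection probability is P(T > t₀.₉₇₅,₁₇₃) for a noncentral t with noncentrality b / 0.1512.

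| Assumed b (SD) | Noncentrality | One-sided error |
|---|---|---|
| 0 | 0 | 2.5% |
| 0.05 | 0.33 | 5.1% |
| 0.10 | 0.66 | 9.6% |
| 0.20 | 1.32 | 26.0% |

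For scale, b = 0.10 would arise if a quarter of ratings in one arm only shifted by 0.4 SD (0.25 × 0.4 = 0.10). The same shift in both arms in the same direction would give b = 0, and opposite shifts would give b = 0.20. Only a difference between arms matters.

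**The case against.** The best defence is that the protocol states physician blinding outright and without restriction, and that its written reporting routes mostly bypass the rater. Device questions go to customer support and then to the principal investigator or manufacturer. Adverse events go through diaries, customer support and SAFTEE. Use of collected self-report data by the physician is described for the baseline visit only. All of this stands. What it leaves open is narrower: no procedure stops disclosure at the visit itself.

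Two stronger readings are tempting, and the documents support neither.

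- *The HAM-D rater receives the participant's self-report scores through the alerts.* The alerts go to oversight staff. That the individual rater is among them is an inference from joining the Study Design section with the oversight section. Alerts fire only above 20 and do not reveal the arm.
- *The blinding statement covers shipment records only.* It is worded generally. The fair criticism is that fulfillment is the only mechanism described.

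It can also be said that the order of steps within a visit and rater screen settings often sit in rater instructions, and that this is a protocol summary. That lowers the weight of the point. It does not settle the unblinding conflict, which lies in the protocol's own text.

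**Conclusion.** The concern holds in limited form. The protocol combines clinical care and HAM-D rating in one physician role, states blinding, and gives no safeguard against arm-suggestive disclosure before the rating. Separately, its passages on when the blind ends contradict each other, and the week-4 visit is not placed before the unblinding. This second gap is the more firmly documented, because it rests on the text and not on what a participant might say.

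The size is unknown. The error rates of about 5.1% to 26.0% depend wholly on an assumed between-arm rating bias of 0.05 to 0.20 SD and show sensitivity, not expectation. They concern a secondary outcome; a reader might infer that the primary result is compromised, but the rater's role does not touch the self-reported BDI comparison. What is at stake is how much weight the HAM-D can carry as independent support. This is an inexpensive improvement to make before the rating visits begin.

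**What to change.** 1. Reconcile the passages on unblinding (week 4 in Study Design, end of study in Study Design/Methods) with the visit window, so that each participant's week-4 HAM-D is completed and locked before that participant is unblinded.
2. State that, within the visit, the HAM-D is completed and locked before any discussion of the device or adverse events, and that participants are asked not to describe device sensations until then.
3. State that the rater's view shows no follow-up PHQ-8, BDI, diary, SAFTEE or support data until the rating is locked.
4. Leave the safety alerts unchanged.
5. Record whether the rater had earlier alert or adverse-event contact with the participant, and report this descriptively by arm. Do not exclude those participants from a HAM-D analysis: alerts and adverse events occur after randomization and may relate to outcome and device, so exclusion could hide or create a difference.

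**Cost.** A short visit instruction, a platform view setting, one recorded item and one descriptive table, with no extra raters. The downsides are a fixed visit order and incomplete shielding where a rater has already handled an alert.

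### The week-2, week-4 and week-8 assessments start only when a participant reports a completed first treatment, with no fallback date for randomised people who never report one

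*Protocol*

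**What the plan says.** Treatment Instructions gives the order of events. Once a prescription is issued, "the patient is randomized to either an immediate or delayed treatment arm, and delivery of the Fisher Wallace device will be made", so allocation precedes any contact with the device. The same section sets the clock: "The study timeline will commence upon completion of the first treatment as identified by the participant in ProofPilot".

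Study Design/Methods describes the platform step. The Start the trial "task will trigger the 2 week, 4 week and 8 week follow up points key to the outcome measures". For the physician assessment, at which the HAM-D is done, it adds: "It will also trigger the window period for the final (week 4) participant/physician video teleconference assessment". Participant Compensation confirms that this task and the first treatment are the same event, since the first payment covers "Baseline through completing first Fisher Wallace Treatment (aka 'Start Task').

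No other trigger for these assessments is described, although Study Design/Methods says that carrier tracking, including the delivery event, already releases tasks in ProofPilot.

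The control arm receives "a sham device that looks exactly the same, but only provides treatment for 2 seconds" (Study Design). The primary outcome is the change in BDI from baseline to treatment week 4. Statistical Analyses compares the randomised groups by t-tests on change from baseline and mentions missing data only as a sensitivity analysis.

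**The concern.** The event that opens outcome collection comes after randomisation, depends on the participant's own report, and is completion of a session, not receipt of the device. Someone may be randomised, shipped a device and perhaps try it, yet not log a completed first session. That person gets no week-4 BDI or PHQ-8 request and no physician window for the HAM-D. The scheduled COMBINE SAFTEE runs on the same clock.

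This differs from ordinary dropout in two ways. The outcome is not refused or lost; it is never requested. And the step at which people are lost can follow exposure to devices that behave differently: one is used for a 20-minute session, the other delivers current for 2 seconds. Discomfort, or an impression that nothing is happening, could then affect who logs a start, and could do so unequally.

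Study Design says that weeks 1-4 are meant to support a premarket approval submission, so the week-4 randomised comparison is the one that most needs to cover everyone randomised.

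**Working it through.** **1. Sequence.** Prescription, then randomisation, shipment, tracked delivery, participant-reported first treatment, and finally the week-2, week-4 and week-8 clock. Baseline BDI and PHQ-8 are collected at enrolment, before randomisation. A non-starter therefore has a baseline but no scheduled week-4 value, and so no change score.

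**2. The plan's own figure.** Sample Size gives 175 in total, 1:1, one-sided alpha 0.025, 80% power and effect size 0.426. That section names PHQ-8 as primary while Primary Outcome Measures names the BDI; the check is in SD units, so this does not affect it.

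- Normal approximation: n per arm = 2 × (1.960 + 0.842)² / 0.426² = 86.5, so 87 per arm and 174 in total.
- Noncentral t: 88 per arm, 176 in total. Power at 88 + 87 is 80.0%.

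The figure reproduces, with all 175 analysed and no allowance for loss.

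**3. Bias from unequal non-start.** The protocol gives no non-start rates, so those below are assumptions. Let f be the non-start rate in an arm, and suppose non-starters would have improved k SD less than starters in the same arm, with k equal in both arms. The whole-arm mean improvement is μ = (1 − f) × S + f × (S − k), where S is the starters' mean. Hence S = μ + f × k. The shift in the starter comparison is k × (difference in f), in favour of the arm that loses more. If non-starters would have done better, the sign reverses.

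| Assumed non-start, one arm vs the other | k | Shift | Share of 0.426 |
|---|---|---|---|
| 10% vs 10% | 0.5 SD | 0 | 0 |
| 10% vs 5% | 0.5 SD | 0.05 × 0.5 = 0.025 SD | about 6% |
| 20% vs 5% | 0.5 SD | 0.15 × 0.5 = 0.075 SD | about 18% |

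**4. Effect on the test if the shift happens to favour active and there is no true effect.** The standard error in SD units is √(1/n₁ + 1/n₂), with n = 87.5 × (1 − f), and the rejection probability is 1 − Φ(1.960 − shift/SE).

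- 10% vs 5%: n = 78.75 and 83.125, SE = 0.157. One-sided type I error is about 0.036 instead of 0.025.
- 20% vs 5%: n = 70 and 83.125, SE = 0.162. One-sided type I error is about 0.067.

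If the shift favours sham, the test is conservative instead.

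**5. Power with non-starters excluded or kept.** Excluding them reduces n and leaves the effect at 0.426. Keeping them holds n at 175; if those in the active arm get no device effect and the SD is unchanged, the effect becomes 0.426 × (1 − f). Both columns use the noncentral t at one-sided 0.025, with equal non-start in the two arms.

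| Non-start | Excluded | Kept |
|---|---|---|
| 5% | 166 analysed, 77.9% | effect 0.405, 75.9% |
| 10% | 158 analysed, 75.8% | effect 0.383, 71.3% |

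Keeping unexposed participants costs more power than excluding them.

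**The case against.** The strongest reply is that arm-related loss at this step is conjecture. The trigger is the participant's own statement, and no device log or verified full session is required, so someone who stopped early may still mark the task done. No deadline is stated, so a failed first attempt can be repeated. The devices look alike, participants are described as blinded, delivery releases instructions and a prompt to start, and the first payment depends on the Start Task. All of this works against loss, and against unequal loss. It stands as a limit on the likely size of the problem. It does not supply an outcome for anyone who still logs nothing.

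A second reply is that timing week 4 from first use is sensible for a mailed device because it aligns exposure. That also stands, and the fix keeps it for everyone who logs a start.

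A third is that the analysis set and the handling of missing data belong in the SAP, which is not shown. That is right for the analysis rule. The trigger, however, is a data-collection rule in the protocol, and a SAP cannot recover values that were never requested.

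A reader might also draw stronger conclusions, which the protocol does not support:

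- *All follow-up is lost.* The daily diary and adverse events reported through customer support are not tied to the Start Task.
- *The protocol excludes non-starters.* It states no such rule; their absence follows from the workflow.
- *No analysis could include them.* Baseline scores exist, so imputation is possible, but only under untestable assumptions.
- *The fix protects power.* The last table shows the opposite.

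**Conclusion.** The gap in the protocol is certain. The scheduled outcome assessments and the week-4 physician window depend on a participant-reported event after randomisation, and there is no fallback. Its consequence is uncertain. Differential non-start is possible because the trigger is session completion and the sham runs for 2 seconds, but nothing in the protocol shows that it will occur, how large it would be or which arm it would favour.

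Under the assumed rates and a 0.5 SD deficit common to both arms, the bias runs from zero (equal rates) through about 6% of the design effect (10% versus 5%) to about 18% (20% versus 5%). A reader might infer that the primary result is necessarily biased towards the device; neither the sign nor the size can be established from the protocol. This is a worthwhile, inexpensive improvement to data collection. It does not show that the trial's comparison is invalid.

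**What to change.** Keep the reported first treatment as the clock for participants who log one. Add to Treatment Instructions and Study Design/Methods that, if none is logged within a fixed number of days of the tracked delivery scan, that participant's assessment clock starts on that date. Send the week-2 and week-4 BDI and PHQ-8 and the week-4 HAM-D invitation on that clock. State in advance which clock governs if a first treatment is logged later. The fallback should govern assessments only and leave device use as planned. Report the number of non-starters by arm. How these participants enter the primary analysis can be left to the SAP.

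The cost is one more platform trigger, using tracking data that ProofPilot already receives, and a short protocol addition. If these participants are kept in the primary analysis, the contrast is diluted: power is about 75.9% at 5% unexposed and 71.3% at 10%, against 77.9% and 75.8% if they are excluded. That loss is the price of a comparison that covers everyone randomised, and the sponsor should accept it knowingly.
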